**Table 2. Safety Summary Time Periods**

Time Period	Study Day Range	
	AE Onset	Other Safety Measurement
Baseline	N / A	Last value on or before the first dose
First 4 weeks	1* - 28	2* - 28
1 – 3 months	29 – 91	29 – 91
>3 – 6 months	92 – 183	92 – 183
>6 – 12 months	184 – 365	184 – 365
>1 – 2 years	366 – 730	366 – 730
>2 – 3 years	731 – 1095	731 – 1095
>3 – 4 years	1096 – 1461	1096 – 1461
>4 years	>= 1462	>= 1462

\* Protocol procedures specified that all baseline assessments were to be done before administration of study drug on Day 1. For conservative reason, AEs started on Day 1 are considered “post-baseline”.

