## 5.7 Study Drug Exposure and Overall Compliance

### 5.7.1 Study Drug Exposure

For the final CSR, all subjects' study drug (pimavanserin) exposure will be calculated as last dose date minus first dose date + 1. For the interim report(s), the drug exposure will be censored at the database snapshot date for the on-going subjects. For example, if a subject had withdrawn from the study before the database snapshot, then the exposure duration for this subject is last dose date minus first dose date + 1; if a subject was still ongoing at the database snapshot date, then the exposure duration for this subject is database snapshot date minus first dose date + 1.

A summary of study drug exposure will include the duration of exposure as a continuous measure in days and a categorical measure for the intervals (1-28 days, 29-91 days, 92-183 days, 184-365 days, 366-730 days, 731-1095 days, 1096-1461 days,  $\geq 1462$  days). Total amount of administered pimavanserin (mg) will be estimated by (duration of exposure\*40 mg). Study drug exposure by Sponsor re-classified termination reasons will also be summarized. Study drug exposure for subjects who died will also be summarized.

Study drug exposure measures as described above will be presented in a listing.

Since this is an open-ending study, time on pimavanserin treatment (time on study) will be evaluated for all subjects and by subgroups: baseline age group ( $\leq 75$  years old or  $> 75$  years old), gender (female or male), and geographic area (North America or outside North America). For subjects who have discontinued from study, the days on pimavanserin treatment in study -015 (not counting the exposure duration from the preceding study) will be calculated as last dose date minus first dose date + 1; otherwise the time on study will be censored at database snapshot date and will be calculated as database snapshot date minus first dose date + 1. Kaplan-Meier estimates of percent subjects on treatment at 6 months (183 days), 1 year (365 days), 1.5 years (548 days), 2 years (730 days), 2.5 years (913 days), 3 years (1095 days), 3.5 years (1278 days) and 4 years (1461 days), as well as median days on treatment will be presented.

In addition, Kaplan-Meier estimates percent subjects free of AEs leading to study termination or drug withdrawal and median days to due to AEs leading to study termination or drug withdrawal will be summarized for all subjects and by

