### 5.13.1 Adverse Events

AEs started between first study dose date and 30 days after the last dose date will be considered treatment-emergent AE (TEAEs). Any AEs with a completely missing start date will be considered as TEAEs. All AEs and TEAEs will be summarized. In addition, the number of TEAEs, and the number and percent of unique subjects with TEAEs will be summarized by system organ class (SOC) and preferred terms. For SAEs, the SAE onset date will be used in place of the AE onset date for the determination of treatment-emergent status and for assignment of the event to time windows and onset age groups.

AEs will be summarized in terms of the proportion of subjects as well as number of events. When calculating the proportion of subjects with AEs by time period or age group each subject will be counted in the numerator at most once and any repetitions will be ignored; the denominator will consist of all safety-evaluable subjects in the specified time period or age group. When calculating the number of events, each unique record in the database will be counted once.

Additional summaries of TEAEs will also be tabulated with respect to severity (mild, moderate, severe) and AEs of special interest. Tabulations will also be provided for AEs by maximum severity where a subject with more than one event coded to the same preferred term will be classified according to the most severe event. Similarly, in the tabulation by strongest relationship, a subject will be classified according to the event with the strongest relationship to study drug.

An overall summary of all AEs and TEAEs will be presented. The number and percent of unique subjects with TEAEs will be summarized by system organ class (SOC) and preferred term. The number and percent of unique subjects with TEAEs that are determined by investigators as related (possibly, probably, or definitely) to study drug will also be summarized by SOC and preferred term. Additional summaries of TEAEs will also be tabulated with respect to severity (mild, moderate, or severe), where a subject with more than one event coded to the same preferred term will be classified according to the more severe event. A summary of TEAEs in descending order of frequency by preferred term will also be tabulated. Listings of deaths, serious AEs and AEs leading to study treatment discontinuation will also be provided.

The tabulation of TEAEs will be grouped by (1) time period at AE onset and (2) age at AE onset.

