- (1) AEs grouped by time period at AE onset: For all TEAEs, serious TEAEs, TEAEs leading to discontinuation of study drug, and TEAEs of special interest (those that may be expected on the basis of pimavanserin's pharmacology, those of special regulatory interest [suicidality, abuse liability etc], and those commonly associated with current antipsychotics), the count and percentage of subjects will be summarized by time period defined in [Section 5.4.2 Table 2](#). The denominator for a time period will be the number of subjects on treatment

(including a 30-day follow-up) during that particular time period. TEAEs with fatal outcome will be summarized by time period at death.

- (2) AEs by age group at AE onset: For all TEAEs, serious TEAEs, TEAEs leading to discontinuation of treatment, and TEAEs of special interest, the count and percentage of subjects will be summarized by age category at the time of AE onset. Age at onset will be categorized as follows:  $\leq 50$  years, 51 - 60 years, 61 – 70 years, 71 – 80 years and 81 - 90 years. The denominator for an age group will be the number of subjects on treatment (including a 30-day follow-up) while in that particular age group. TEAEs with fatal outcome will be summarized by age group at death.

An AE listing by subject will display all events and will include the verbatim term in addition to the MedDRA SOC and preferred term. This listing will also include all relevant CRF data associated with the event: date of onset, date of last dose, severity, outcome, relationship to study drug, action taken, and seriousness.

In addition, AE tables also will be summarized by age group and onset time period for subject with concomitant antipsychotic use and without antipsychotic use.

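### Adverse events by onset period are shown only as counts and head-count percentages over periods of 28 to 366 days and an open-ended last one, so early and late periods cannot be compared directly

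*SAP*

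**What the plan says.** SAP 5.13.1 item (1) tabulates four groups by onset period: all TEAEs, serious TEAEs, TEAEs leading to discontinuation, and TEAEs of special interest. The display is the number and percentage of subjects. On the denominator the SAP says "The denominator for a time period will be the number of subjects on treatment", and the same sentence continues "including a 30-day follow-up) during that particular time period". In the numerator, "each subject will be counted in the numerator at most once and any repetitions will be ignored". Event counts are also planned ("When calculating the number of events, each unique record in the database will be counted once"), without a time denominator.

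The periods are those of SAP 5.4.2, "Table 2. Safety Summary Time Periods". For AE onset they are days 1-28, 29-91, 92-183, 184-365, 366-730, 731-1095 and 1096-1461, then day 1462 onward.

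Some time-based analysis is planned. SAP 5.7.1 has "Kaplan-Meier estimates of percent subjects on treatment at 6 months" and later half-yearly points, and "Kaplan-Meier estimates percent subjects free of AEs leading to study termination or drug withdrawal". SAP 5.13.2 has Kaplan-Meier survival. SAP 5.5 reports the number of subjects remaining at the start of each period, and 5.7.1 summarizes duration of exposure. Neither document mentions patient-years or exposure-adjusted rates.

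**The concern.** The only objective is long-term safety and tolerability, and there is no control arm, so the pattern of events over time is a main result. A percentage of subjects with at least one event grows with the length of the window, even if risk never changes. The windows differ about 13-fold in length (366/28 = 13.1). The head count also gives a subject present for one day of a period the same weight as one present throughout.

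Read across the row, the table can suggest that risk rises with time on drug when it is flat, and a modest early excess can go unnoticed. Discontinuation events and deaths have Kaplan-Meier estimates to set beside the percentages. All TEAEs, serious TEAEs and TEAEs of special interest do not.

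**Working it through.** **Inputs from the documents.** Period lengths (last day minus first day plus 1, Table 2): 28, 63, 92, 182, 365, 365 and 366 days, which sum to 1461. Follow-up after last dose: 30 days (SAP 5.13.1). Anticipated enrolment: at least 400 (protocol 3.4). The plan states no figure to reproduce here.

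**Assumptions.** Constant event rate h from 0.02 to 5 per year; constant discontinuation rate d from 0 to 1.0 per year; deaths and the snapshot cut-off ignored.

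**Expected percentage**, with T the period length in days divided by 365.25:
- First 4 weeks: 1 - exp(-hT). The 30-day follow-up outlasts the period, so d has no effect.
- Months 1-3: two days fully at risk, then h/(h+d) x [1 - exp(-(h+d) x 61/365.25)] among those still event-free.
- Later closed periods: h/(h+d) x [1 - exp(-(h+d)T)].

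**Flat risk, h = 0.3 per year:**

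| Period (days) | 28 | 63 | 92 | 182 | 365 | 365 | 366 |
|---|---|---|---|---|---|---|---|
| d = 0 | 2.3% | 5.0% | 7.3% | 13.9% | 25.9% | 25.9% | 26.0% |
| d = 1.0 | 2.3% | 4.7% | 6.4% | 11.0% | 16.8% | 16.8% | 16.8% |

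Total events per 100 patient-years would be 30 in every column.

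**Ratio of >1-2 years to first 4 weeks, no change in risk:**
- h = 0.02: 12.9 (d = 0) to 8.2 (d = 1.0)
- h = 0.3: 11.4 to 7.4
- h = 5: 3.1 to 2.6 (at d = 1.0, 83.1% against 31.8%)

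The upper end is essentially the ratio of lengths, 365/28 = 13.0.

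**Early excess.** Take 0.9 per year in the first 4 weeks and 0.3 afterwards. The first period shows 1 - exp(-0.9 x 28/365.25) = 6.7%. Months 1-3 show 5.0% (4.7% with d = 1.0), so the excess is visible there. Year 2 shows 25.9% (16.8%), which still looks higher. With d = 0, the first period exceeds months 1-3 only if the excess is above 63/28 = 2.25-fold. With d = 1.0 and h = 0.3 the threshold is -ln(1 - 0.0466)/(0.3 x 28/365.25) = 2.1.

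**Open period.** At 0.2 events per year, the >4-year percentage is 1 - exp(-0.2 x 0.25) = 4.9% after 0.25 year of follow-up and 1 - exp(-0.2 x 4) = 55.1% after 4 years.

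**What can be rebuilt.** Averaging successive period-start counts and multiplying by period length approximates patient-years. For d of 0.25 to 1.0 this is within 8% of exact at-risk time (30-day follow-up included) in every closed period.

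**Choice of rate and interval.** Suppose each subject's rate is constant but rates vary between subjects (assumed gamma, shape 1).
- Mean 3 per year, d = 0: a first-event rate restarted in each period falls from 271 to 162 per 100 patient-years between the 28- and 365-day periods. The total-event rate stays at 300.
- Mean 0.3 per year, d = 0: the first-event rate falls only from 29.7 to 26.4.
- Simulated coverage (400 subjects, 365 days, d = 0.5): at mean 3 per year a plain Poisson 95% interval covers about 68% and a subject-level robust interval about 95%; at 0.3 per year, 92% and 95%.

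**Imputed dates.** SAP 5.4.3 generally sets fully missing onset dates, and partial ones in the month or year of first dose, to day 1. With 400 subjects the first period holds 400 x 28/365.25 = 30.7 patient-years, so one such record adds 100/30.7 = 3.3 per 100 patient-years. In a full one-year period one record adds 100/399.7 = 0.25.

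**The case against.** The plan is descriptive, and no passage says the percentages will be compared across periods or tested for trend. Table 2 prints the day ranges. Each percentage is a valid description of its own period. The three one-year periods, which carry much of the long-term question, are nearly equal in length. Discontinuation events and deaths already have Kaplan-Meier estimates. All of this stands, and it confines the problem to reading early periods against late ones and to the open period.

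A reader might go further in two ways that the documents do not support. One is that the table would hide any early excess, even a large one. It would not: a threefold excess shows as a higher percentage in 28 days than in the following 63. The other is that rates cannot be recovered at all. For the closed periods they can be approximated from the period-start counts in SAP 5.5 and the planned event counts. Exact rates, confidence intervals and the >4-year period remain out of reach.

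It can also be said that a rate for a 28-day period magnifies records imputed to day 1. That is correct, and the fix has to deal with it.

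**Conclusion.** The point holds within those limits. For all TEAEs, serious TEAEs and TEAEs of special interest, the onset-period tables carry no time denominator, and percentages from short and long periods are not directly comparable. Under the assumed rates, flat risk gives a year-2 percentage 2.6 to 12.9 times that of the first 4 weeks. The multiple is largest for rare events with little discontinuation and smallest for very common events with heavy discontinuation. No combination in the range removes it. An early excess below about 2.25-fold (about 2.1 with discontinuation of 1.0 per year at 0.3 events per year) would not stand out even against months 1-3.

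These sizes rest on assumed constant rates; the period lengths and the missing person-time denominator do not. The planned tables are incomplete for comparison over time, not wrong. The age-at-onset table also uses a head count ("The denominator for an age group will be the number of subjects on treatment (including a 30-day follow-up) while in that particular age group"), but the direction of any distortion there is unknown.

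**What to change.** Keep the planned counts and percentages. In SAP 5.13.1 item (1), add for each onset period:

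- Patient-years at risk: time on treatment plus 30 days, cut at death, snapshot date and period end.
- Total events per 100 patient-years, with a 95% interval that allows for repeated events within a subject, for example by a subject-level robust variance.
- Optionally, for serious TEAEs and TEAEs of special interest, subjects with a first event in the period per 100 patient-years, with at-risk time stopped at that event. For common events this measure can itself fall with period length.

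Add three footnotes:

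- Events are AE records. Under protocol 6.2.7.1 a change in severity can end one record, and recurrent episodes of the same severity can share one.
- Later periods describe those who stayed; a rate does not remove selective drop-out.
- Onset dates imputed to day 1 fall in the first period. Show that period's rate with and without those records.

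The cost is SAP wording, some programming from dates already collected (first dose, last dose, onset, death) and larger tables. No new data are needed.

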### **5.13.2 Deaths and Other Serious and Significant Adverse Events**

Treatment-emergent SAEs, TEAEs leading to discontinuation from the study or study drug, and TEAEs with fatal outcome will be summarized by time period as given in [Table 2](#) in frequency tables by SOC and preferred term. In addition, the overall AE summary table will also be presented for all events (i.e. treatment-emergent plus non-treatment-emergent events).

Subject listings of SAEs, deaths, and AEs leading to discontinuation of study drug will be provided. These listings will provide all relevant eCRF data for each event including the date/study day of onset, date/study day resolved, date of last dose/study day of last dose, severity, outcome, relationship to study drug, action taken, and seriousness.

Kaplan-Meier estimates of percent surviving subjects at 6 months, 1 year, 1.5 years, 2 years, 2.5 years, 3 years, 3.5 years and 4 years, as well as median survival time will be computed for all subjects and by subgroups: baseline age group ( $\leq 75$  years old or  $>75$  years old), gender (female or male), and geographic area (North America or outside North America). If a subject is deceased, the survival time will be calculated as death date minus first dose date + 1; otherwise the survival time will be censored at the last dose date (for subjects who have discontinued from the study) or database snapshot date (for ongoing subjects).

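### Fatal TEAEs are filed by period or age at death, but the stated denominator stops 30 days after last dose, so a late death can fall in a column whose denominator excludes that subject

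*SAP*

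**What the plan says.** SAP 5.13.1 makes an event treatment-emergent by its start date, from first dose to 30 days after last dose. It sets no limit on the date of death. For SAEs, the same section uses the SAE onset date to decide treatment-emergent status and to place the event in time windows and onset age groups. Under the SAP Definitions, any AE that results in death is an SAE.

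Item (1) then says "The denominator for a time period will be the number of subjects on treatment", extended by a 30-day follow-up, in that period. The next sentence reads "TEAEs with fatal outcome will be summarized by time period at death". Item (2) follows the same pattern: "The denominator for an age group will be the number of subjects on treatment (including a 30-day follow-up) while in that particular age group", and then "TEAEs with fatal outcome will be summarized by age group at death". The section's general statement is that "the denominator will consist of all safety-evaluable subjects in the specified time period or age group". It gives no separate rule for deaths.

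SAP 5.13.2 adds that "TEAEs with fatal outcome will be summarized by time period as given in" Table 2, in frequency tables by SOC and preferred term.

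Protocol 6.2.7 has AEs followed until they resolve, stabilize, are otherwise explained or cease to be clinically significant, or the subject is lost to follow-up. It sets no 30-day cap, and death is one of the AE outcomes recorded (Protocol 6.2.7.1).

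**The concern.** For every other TEAE the date that chooses the column is the onset, and the onset lies inside the same 30-day window that defines the denominator. Numerator and denominator therefore match. Fatal TEAEs alone are placed by a later date that the window does not bound. A subject whose event began on drug, but who died after the window closed, can be counted in a period or age group in which the SAP no longer counts them as at risk. That cell is then not a proportion of its own denominator.

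The at-death rule also sits beside a general SAE-onset rule in the same section without being called an exception. A programmer has to decide which governs, and the fatal rows need not be a subset of the serious rows in the same column. Long-term safety is the study's only objective (SAP 3.1), so the fatal-event tables will be read closely even if few cells are touched.

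**Working it through.** The plan gives no figure on this point (SAP 2.4 lists sample size as not applicable), so there is none to reproduce. The check applies the rules to the Table 2 boundaries.

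**Inputs**
- Period start days, SAP Table 2: 1, 29, 92, 184, 366, 731, 1096, 1462.
- Treatment-emergent window and denominator window: both end at last dose + 30 days (SAP 5.13.1).
- L = day of last dose, O = onset day of the serious event, D = day of death, P(x) = period containing day x.

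**Rule.** The event is a TEAE if O ≤ L + 30. The subject is in the denominators up to P(L + 30). The fatal event is filed in P(D). A mismatch occurs when P(D) is later than P(L + 30), that is, when a period starts after L + 30 and on or before D.

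| L | O | D | L + 30 | Last denominator period | Column for the death | Subject in that denominator? |
|---|---|---|---|---|---|---|
| 60 | 58 | 130 | 90 | 1–3 months | >3–6 months | No |
| 330 | 355 | 370 | 360 | >6–12 months | >1–2 years | No |
| 330 | 355 | 362 | 360 | >6–12 months | >6–12 months | Yes |
| 345 | 360 | 370 | 375 | >1–2 years | >1–2 years | Yes |
| 88 | 88 | 95 | 118 | >3–6 months | >3–6 months | Yes |

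The last row has no denominator problem but shows the second issue. By SAE onset the event is in 1–3 months in the serious-TEAE table; by date of death it is in >3–6 months in the fatal table.

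**How often a late death would cross a period boundary.** The lag is assumed, and last dose is assumed equally likely on each day of the period. Worked case: last dose in Days 29–91 and death 60 days later needs L + 30 ≤ 91 and L + 60 ≥ 92, so L = 32 to 61, which is 30 of 63 days.

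| Last dose in | Death 60 days after last dose | Death 90 days after last dose |
|---|---|---|
| Days 29–91 | 30/63 = 48% | 33/63 = 52% |
| Days 92–183 | 30/92 = 33% | 60/92 = 65% |
| Days 184–365 | 30/182 = 16% | 60/182 = 33% |
| Days 366–730 | 30/365 = 8% | 60/365 = 16% |

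For shorter lags, let g be the days from the end of the 30-day window to death. Over last-dose days 1–1461, six boundaries (92 to 1462) can be crossed, so the share is 6g/1461. Over last-dose days 1–365, three can be crossed, so the share is 3g/365.

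| g | Last dose Days 1–1461 | Last dose Days 1–365 |
|---|---|---|
| 7 | 42/1461 = 2.9% | 21/365 = 5.8% |
| 14 | 84/1461 = 5.7% | 42/365 = 11.5% |
| 30 | 180/1461 = 12.3% | 90/365 = 24.7% |

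These are shares of possible last-dose days among deaths that already fall outside the window. They are not predicted death rates.

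**Age table.** The bands from 51–60 to 81–90 are ten years wide, about 3,652 days. If age is uniform within a band, the chance of crossing a boundary in g days is g/3652: 30/3652 = 0.8% and 90/3652 = 2.5%.

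**Effect of one affected death.** It adds 1/N to the cell. N by period is not given. For assumed N of 100 to 200 this is 1.0 to 0.5 percentage point; for assumed N of 300 to 400 it is 0.33 to 0.25. Protocol 3.4 anticipates at least 400 subjects enrolled.

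**Filing by onset.** Since O ≤ L + 30 by definition, P(O) is never later than P(L + 30). Enumerating L from 1 to 1499 with every O from 1 to L + 30 gives 0 mismatches.

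**The case against.** The case for leaving the text alone has several parts.

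- **The conditions are narrow.** A mismatch needs onset by last dose + 30, death after it, and a boundary in between. If death comes by last dose + 30 there are no cases. Protocol 6.2.7 lets follow-up end at stabilization or loss to follow-up and does not oblige investigators to seek AE information from former participants, so such deaths may rarely be recorded. This stands.
- **The onset view is already planned.** Every fatal TEAE is a serious TEAE, and those are tabulated by onset period and onset age. A reader might infer that deaths from events begun on drug are moved out of the exposure period altogether. The documents do not support that: only the separate fatal summary moves them, and the overall fatal total is unchanged.
- **Filing at death looks deliberate.** It is written twice and shows when deaths occurred. The Kaplan-Meier survival estimates in SAP 5.13.2 start at 6 months, so they do not replace it for the early periods. This stands, and the fix has to allow for it.
- **SAP 5.13.2 is not a clear contradiction.** A reader might infer that its reference to Table 2, whose AE column is headed by onset, sets a second placement. It can equally be read as supplying only the periods. The firmer conflict is with the SAE-onset rule within 5.13.1.
- **The denominator for fatal rows is inferred.** The count-and-percentage sentence in item (1) does not list fatal TEAEs. The inference is still reasonable: the denominator sentence comes just before the at-death sentence, no other denominator is specified for these tables, and SAP 5.1 summarizes categorical data as number and percentage.

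**Conclusion.** The point holds as a narrow defect in a stated rule. SAP 5.13.1 (1) and (2) can count a fatal TEAE in a column whose denominator excludes that subject, and they depart from the section's SAE-onset rule without saying so. The denominator part rests on reading the stated period and age denominators as applying to the fatal rows.

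The size is small and not known. Only deaths more than 30 days after last dose that also cross a boundary are affected; few are likely, and there may be none. A reader might infer from the 48% and 65% shares that the problem is common, or that fatal-TEAE percentages are generally not proportions. Neither follows. The shares depend on assumed lags of 60 and 90 days among deaths already outside the window, and only a cell containing an affected death is improper. The age table is much less exposed than the period table. The survival analysis, the overall fatal-TEAE totals and the serious-TEAE tables by onset are untouched.

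**What to change.** Amend the two at-death sentences in SAP 5.13.1 (1) and (2) in one of two ways.

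(a) File fatal TEAEs by period and age at SAE onset, with the same denominators as other TEAEs, and show date of death and days since last dose in the death listing. This removes the mismatch by construction. The cost is that period of death is no longer tabulated and has to be read from the listing.

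(b) Keep period and age at death, state that this is an exception to the SAE-onset rule, and give those rows counts only, or a denominator that includes subjects whose fatal TEAE was still being followed in that period or age group. This keeps the sponsor's view of when deaths occurred. Counts are the simpler choice, because the enlarged denominator is partly defined by the outcome.

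Under either option, add a few words to SAP 5.13.2 saying which date places a fatal TEAE in a Table 2 period. The change is to wording and table programming only; no new data are needed beyond the dates of death and last dose.
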